- 2) Two doses of RP-1664 as pediatric sprinkle capsules, one in the fed-state (with a high-fat meal) and one in the fasted-state (RP-1664 sprinkled over soft food), to examine the effect of food on RP-1664 PK, or
- 3) Two doses of RP-1664, one as the adolescent/adult whole capsule and the other as a pediatric sprinkle capsule, to compare the PK of the two formulations.

After completion of Cycle 0, participants will begin C1D1 at the assigned, SRC-approved dose and schedule being tested.

The starting dose (Dose Level 1) is anticipated to be 10 mg once daily (QD), when calculated based on the principles outlined in the International Conference on Harmonization (ICH) S9 Nonclinical Evaluation of Anti-cancer Pharmaceuticals (Section 2.2.6). Since neutropenia has been observed in preclinical safety studies and is an anticipated toxicity in humans, RP-1664 will initially be given QD on a 2 weeks on/1 week off schedule to allow 1 week for bone marrow recovery. Since the projected efficacious dose of RP-1664 in humans is approximately 300 mg QD (based on preclinical models), the first escalation (Dose Level 2) will be up to 30 mg to limit the number of participants receiving a potentially sub-therapeutic dose. After Dose Level 2, escalation will proceed with up to 100% increases in RP-1664 after evaluation of tolerability by

the SRC until Dose Level S. Dose Level S is defined as the dose level at which any of the following safety signals occur during Cycle 0 or Cycle 1:

- Any ≥Grade 3 hematological toxicity, or
- >50% decrease in platelets or neutrophils from Cycle 0 Day 1, or
- >2 g/dL decrease in hemoglobin from Cycle 0 Day 1, or
- Any ≥ Grade 2 drug-related non-hematological toxicity lasting >5 days or requiring clinical intervention, except Grade 2 fatigue, nausea, vomiting, diarrhea, or constipation, or
- Any adverse event (AE) of any grade limiting tolerability as assessed by the SRC

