12.3 Clinical Laboratory Tests

Selected hematology and serum chemistry parameters including Alanine Aminotransferase (ALT), Aspartate Aminotransferase (AST), Creatinine, Total Bilirubin, Hemoglobin, Neutrophiles and Platelets Count will be summarized for Safety population. All other laboratory results, including pregnancy test results, will be listed only.

For all quantitative parameters, the actual value and the change from baseline by scheduled time of evaluation will be summarized by dose levels and dose schedule for each study visit using descriptive statistics. Both scheduled and unscheduled visits will be considered for baseline derivation.

Laboratory parameters are also graded according to CTCAE v5.0 for the selected parameters listed above. A shift table, presenting the 2-way frequency tabulation for baseline and the worst post-treatment value according to the NCI-CTCAE grade, will be provided. Laboratory parameters with CTCAE grading in both high and low directions will be summarized separately. Both scheduled and unscheduled post-treatment visits will be considered in tabulation of the worst post-treatment value. Additionally, the number and percentage of participants with the following potentially clinically significant abnormal liver function test will be presented:

- ALT >3xULN, \geq 5xULN, \geq 10xULN, and \geq 20xULN
- AST >3xULN, \geq 5xULN, \geq 10xULN, and \geq 20xULN
- Total bilirubin >2xULN

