14.1.1 Schedule of Activities

Table 1 Schedule of Activities for Participants Enrolled on 2 Weeks On/1 Week Off Dosing (21-Day Cycles)

						Cyc	e 0														
	Pre- screening						Food Effect or ing Cohorts							Cycle 2			Additional Cycles		EOT/ ET°	Safety	Survival Follow- up ^e
		Screening ^a	Ef For	d (Fo fect) mula l (Pl ridgi	or ation K	Ef Forn	Fasted (Food Effect) or Formulation 2 (PK Bridging)					Cycle	1							Follow -up Visit ^d	
Trial Days	-180 to -1	-28 to -1	1ª	2	3 4	5 (+5)	6	7	8	1ª	1	8 (+2)	15 (+2)	1 (+3)	8 (+2)	15 (+2)	1 (+3) ^g	8 (+2) ^h	Within +7 days of Disc of	30 days after last	Every 90 days (±14 days)
Procedures/ Assessments ^f																			Trt date	dose (+14 days)	
Pre-screen informed consent	X																				
Screening/mai n informed consent		X																			
Inclusion/ exclusion criteria		X	X							X											

	Pre- screening	Screeninga				Cycl	e 0														
			PK	PK Cycle For Food Effe PK Bridging Cohor						PK Cycle ^b									EOT/	Safety Follow	Survival
			Ef For	d (Fo fect) mula 1 (PK ridgin	or tion	Fasted (Food Effect) or Formulation 2 (PK Bridging)				Fasted		Cycle	e 1	Cycle 2				tional cles	EO17	-up Visit ^d	Follow- up ^e
Trial Days	-180 to -1	-28 to -1	1ª	2	3 4	5 (+5)	6	7	8	1ª	1	8 (+2)	15 (+2)	1 (+3)	8 (+2)	15 (+2)	1 (+3) ^g	8 (+2) ^h	Within +7 days of Disc of Trt	30 days after last	Every 90 days (±14 days)
Procedures/ Assessments ^f																			date	dose (+14 days)	
Molecular eligibility ⁱ	X																				
Demographics	X																				
Medical/cance r history		X																			
Physical examination		X	X							X									X		
Abbreviated PE ^j														\mathbf{X}^{j}			\mathbf{X}^{j}			X	
Height ^k		X															X^k				
Weight		X	X							X				X			X		X	X	
Vital sign measurements ¹		X	X							X	X	X	X	X	X	X	X	X ^h	X	X	

							Cycle	e 0														
	-		PK	Cy PK	/cle K Br	For idgi	· Food I ing Coh	Effe	ct o	r	PK Cycle ^b							Additional		EOT/	Safety	Survival
	Pre- screening	Screening ^a	E1 For B1	1 (P ridg	t) or latio 'K jing)	Fasted (Food Effect) or Formulation 2 (PK Bridging)				Fasted		Cycle	:1	Cycle 2				tional cles	ET°	Follow -up Visit ^d	Follow- up ^e	
Trial Days	-180 to -1	-28 to -1	1ª	2	3	4	5 (+5)	6	7	8	1 ^a	1	8 (+2)	15 (+2)	1 (+3)	8 (+2)	15 (+2)	1 (+3) ^g	8 (+2) ^h	Within +7	30 days	Every 90 days
Procedures/ Assessments ^f																				days of Disc of Trt date	after last dose (+14 days)	(±14 days)
ECOG or Lansky performance status		X	X								X				X			X		X	X	

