	Pre-		PK	Cycle PK B	For ridgi	Food ling Col	Effect orts	et or	C	PK yclo										Addi	tional	EOT/	Safety Follow-	Survival
	screening	Screening ^a	Ef For	d_(Foo fect) o mulat 1 (PK ridgin	or ion	Fori	fect)	or ition K		aste	ed		C	ycle 1			Сус	ele 2			cles	ET°	up Visit ^d	Follow- up ^e
Trial Days	-180 to -1	-28 to -1	1ª	2 3	3 4	5 (+5)	6	7	8 1	1	2	1	8 (+2)	15 (+2)	22 (+2)	1 (+3)	8 (+2)	15 (+2)	22 (+2)	1 (+3) g	15 (+2) h	Within +7 days of Disc	30 days after last	Every 90 days (±14
Procedures/ Assessments ^f																						of Trt date	dose (+ 14 days)	days)
Pre-screen informed consent	X																							
Screening/mai n informed consent		X																						
Inclusion/exclu sion criteria		X	X						Х	-														
Molecular eligibility ⁱ	X																							
Demographics	X																							
Medical/cancer history		X																						
Physical examination		X	X						Х													X		

						Cycle	e 0																	
	Pre-		PK	Cyc PK	le For Bridgi	Food I	Effec	ct or s		Pl Cyc										Addi	tional	EOT/	Safety Follow-	Survival
	screening	Screeninga	Ef For	ed_(F ffect mul 1 (P) ridgi	or ation K	Forn	ect)	or ation K		Fas	ted		C	ycle 1			Сус	ele 2		Cy		ET°	up Visit ^d	Follow- up ^e
Trial Days	-180 to -1	-28 to -1	1 ^a	2	3 4	5 (+5)	6	7	8	1ª	2	1	8 (+2)	15 (+2)	22 (+2)	1 (+3)	8 (+2)	15 (+2)	22 (+2)	1 (+3) g	15 (+2)	Within +7 days of Disc	30 days after last	Every 90 days (±14
Procedures/ Assessments ^f																						of Trt date	dose (+ 14 days)	days)
Abbreviated PE ^j																X				\mathbf{X}^{j}			X	
Height ^k		X																		X^k				
Weight		X	X							X						X				X		X	X	
Vital sign measurements ^l		X	X							X		X	X	X	X	X	X	X		X	X ^h	X	X	
ECOG or Lansky performance status		X								X						X				X		X	X	
12-lead ECG ^m		X	X			X				X			X			X				X				
Pregnancy test ⁿ		X	X							X						X				X		X	X	
Clinical safety lab tests ^o		X	X							X						X				X		X	X	

						Cycl	e 0																	
	Pre-					Food I				Pl Cyc										Addi	tional	EOT/	Safety Follow-	Survival
	screening	Screeninga	Ef For	ed_(F ffect) mul: 1 (P) ridgi	or ation K	Fori	fect)	or ition K		Fas	ted		C	Cycle 1			Cyo	ele 2			cles	ET°	up Visit ^d	Follow- up ^e
Trial Days Procedures/ Assessments ^f	-180 to -1	-28 to -1	1ª	2	3 4	5 (+5)	6	7	8	1ª	2	1	8 (+2)	15 (+2)	22 (+2)	1 (+3)	8 (+2)	15 (+2)	22 (+2)	1 (+3) g	15 (+2) h	Within +7 days of Disc of Trt date	30 days after last dose (±14	Every 90 days (±14 days)

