CBC with diff. (included in safety lab tests)													X	X	X		X	X			X ^h		days)	
ctDNA whole blood ^p		X^p	Х							X			X				X			Xh	Xh	X		
Tumor biopsy ^{q,r,s}		X^q															Xr					Xs		
Central testing for molecular eligibility ^t	X																							
Archival tumor tissue ^u	X ^t	X																						
RP-1664 dispensed/colle cted					•			•	1	Dispe	ensec	l and	l collec	eted acc	ording i	to Phar	тасу М	anual						
RP-1664 administration ^v			X			X				X			See Se	ection E	Error! R		c e sourc inistrati		ound., I	Dosing a	ınd			

						Cycl	e 0																	
	Pre-					r Food i			r	P. Cyc	K cle ^b									Addi	tional	EOT/	Safety Follow-	Survival
	screening	Screeninga	Et For	ed_(F ffect mul 1 (P ridgi) or ation K	For	fect) or atio K	n	Fas	sted		(Cycle 1			Cy	cle 2			cles	ET°	up Visit ^d	Follow- up ^e
Trial Days	-180 to -1	-28 to -1	1ª	2	3 4	5 (+5)	6	7	8	1ª	2	1	8 (+2)	15 (+2)	22 (+2)	1 (+3)	8 (+2)	15 (+2)	22 (+2)	1 (+3)	15 (+2) h	Within +7 days of Disc	30 days after last	Every 90 days (±14
Procedures/ Assessments ^f																						of Trt date	dose (+ 14 days)	days)
Review of dosing diary ^w												X	X	X		X	X	X		X		X		
PK sample collection ^x			X	X	X y	Xy	X	X	X	Xz	X	X	Xz			Xz	Xz			Xz				
Blood collection (4β- OHC/total cholesterol) ^{aa}		X	х											X				Х			Х			
Urine collection ^{bb}						X																		
Tumor assessments: RECIST or INRC ^{cc}		X^{dd}																	Cycle 1 9 weeks					
Serum tumor markers ^{ee}		X			To be	assesse	d at	leas	t on	се ре	er cyc	le fr	om Cy	cle 0 De	ay 1 ana	l at EO	T (or as	per sta	ndard o	f care s	chedule).		
AE assessment					7	o be co	llect	ed fi	rom	the t	ime o	f IC	F signi	ng; see	Section	Error!	Refere	ence sou	urce no	t found	•			

						Cycl	e 0																	
	Pre-		PK	Cyc PK	le Fo Bridg	r Food l ging Col	Effe hort	ect o	r	P: Cyc	K cle ^b									Addi	tional	EOT/	Safety Follow-	Survival
	screening	Screeninga	Ef For	d_(Fect) ffect) mula 1 (Pl	or ation K	Form	fect mul 2 (P) or latio	n	Fas	ted		C	ycle 1			Сус	cle 2			cles	ET°	up Visit ^d	Follow- up ^e
Trial Days	-180 to -1	-28 to -1	1ª	2	3 4	5 (+5)	6	7	8	1ª	2	1	8 (+2)	15 (+2)	22 (+2)	1 (+3)	8 (+2)	15 (+2)	22 (+2)	1 (+3) g	15 (+2)	Within +7 days of Disc	30 days after last	Every 90 days (±14
Procedures/ Assessments ^f																						of Trt date	dose (+ 14 days)	days)

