- f. **Procedures/Assessments:** Pre-screening for molecular eligibility can take place up to 180 days before first dose of RP-1664. Screening procedures and tumor assessment must be performed within 28 days before first dose of RP-1664.
- g. **CXD1:** The start of a new additional cycle should always coincide with the start of trial drug administration for that cycle. A +3-day window is allowed for the start of new cycles, though cycles should never start early and should be at least 21 days in length. A -2-day window is allowed for the assessments scheduled for the CXD1 visit to enable flexibility with visit scheduling.
- h. **Day 15 of Additional Cycles:** CBC and vital signs to be assessed only on C2 and C3. For Cycle 3, ctDNA should be collected on Day 15 and not on Day 1, however for Cycles 4 and up, ctDNA should be collected on Day 1. Blood samples for 4β-OHC and total cholesterol are only collected up to Cycle 3.
- i. **Molecular Eligibility:** NGS, FISH, or SNP microarray reports will be emailed for central review to confirm molecular eligibility or determine if additional testing is required.
- j. **Abbreviated PE:** Starting at Cycle 2, abbreviated PE to be performed every 2 cycles (unless full PE necessary by Investigator judgment).
- k. **Height:** Pediatric participants will have their height measured every 3 cycles.
- 1. Vital Signs: Blood pressure, heart rate, and temperature to be measured after the participant has been sitting for 5 minutes.
- m. ECG: 12-lead ECGs to be done in triplicate ≥ 1 minute apart per Table 10. The triplicate ECG measurements must occur within a 30 minute time period. Participants should be in supine position and resting for at least 10 minutes before trial-related ECGs. QTcF should be recorded (QTcB is not required). Participants in the food effect or PK bridging portion of the trial should have ECGs collected per Table 11 and Table 12, respectively.
- n. **Pregnancy Test:** For women of childbearing potential, a serum pregnancy test is required at Screening. If a pregnancy test was done within 96 hours of Cycle 0 Day 1, repeat testing is not required. A serum or urine pregnancy test must be performed on Day 1 of each cycle starting on Cycle 2, at EOT, and at Safety Follow-up visit. A pregnancy test can be performed more frequently if required per local regulations.

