- o. Clinical Safety Laboratory Tests: Clinical laboratory tests (including serum or plasma chemistry, hematology [including reticulocyte count], and urinalysis) will be performed at local laboratories according to the laboratory's normal procedures. See Section Error! Reference source not found. for a complete listing of laboratory tests to be performed.
- p. ctDNA Whole Blood: Blood can be collected as 30 mL at Screening and 30 mL at C0D1, for a total of 60 mL. Blood can be collected either pre- or post- dose for all ontreatment timepoints. After Cycle 4, if CXD1 was delayed (eg, due to an AE), ctDNA sample should be collected at actual cycle visit. For visit prior to Cycle 4, if CXDX is delayed, ctDNA should be collected both at planned and actual cycle visit. Please refer to Lab Manual for guidance on sample collection.
- q. **Baseline Tumor Biopsy:** If archival tissue does not meet trial requirements, a pre-treatment biopsy is mandatory prior to enrollment. If the participant is providing a paired biopsy, a pre-treatment and an on-treatment biopsy are mandatory. Biopsy tissue must be shipped to the Sponsor-designated lab during Screening or by Cycle 1 Day 1 (+7 days). Bone tissue is not acceptable for tumor tissue submission because bone biopsies require a decalcification step that will interfere with downstream processing of the sample. *US only:* Participants 12 to 17 years of age are not required to provide a biopsy.

- r. **On-treatment Tumor Biopsy**: This assessment applies only to participants providing a paired biopsy. Biopsy should be collected on Cycle 2 Day 8 (+2), 2 to 6 hours after dosing of RP-1664. Participants must have taken a minimum of 7 consecutive days of RP-1664 prior to on-treatment biopsy collection. If biopsy collection at this timepoint is not possible, please contact the Sponsor to schedule appropriate time for on-treatment biopsy.
- s. **Post-Progression Tumor Biopsy:** An optional tumor biopsy will be requested post-progression for participants with prior confirmed responses or stable disease ≥ 16 weeks.
- t.
- u. Mandatory Archival Tumor Tissue: Archival tissue is to be submitted to the Sponsor-designated lab during Screening. Refer to Laboratory Manual for further details. If adequate archived tumor tissue is not available and/or a fresh biopsy cannot be safely performed, the participant may still be eligible with prior Sponsor approval. The Sponsor prefers archival material from the primary tumor if available.

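### Table 9 (2 weeks on/2 weeks off) lists a Cycle 2 Day 22 visit with no assessment marked, and after Cycle 1 no routine blood count falls 4 to 12 days after the last dose

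*SAP*

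**What the plan says.** SAP 14.1.1 gives one schedule of activities per dosing schedule. Table 9 covers 2 weeks on/2 weeks off in 28-day cycles and is used only if that schedule is opened. Its headers list Days 1, 8, 15 and 22 in both Cycle 1 and Cycle 2, then Days 1 and 15 in additional cycles.

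- The row "CBC with diff. (included in safety lab tests)" is marked at Cycle 1 Days 8, 15 and 22, at Cycle 2 Days 8 and 15, and at additional-cycle Day 15.
- The row "Vital sign measurements" is marked at Days 1, 8, 15 and 22 of Cycle 1 but only at Days 1, 8 and 15 of Cycle 2.
- The full safety panel, "Clinical laboratory tests (including serum or plasma chemistry, hematology [including reticulocyte count], and urinalysis)", falls on Day 1 of each cycle from Cycle 2.
- Footnote h is headed "Day 15 of Additional Cycles" and reads "CBC and vital signs to be assessed only on C2 and C3".

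The natural comparator is Table 1, "Schedule of Activities for Participants Enrolled on 2 Weeks On/1 Week Off Dosing (21-Day Cycles)". It has counts at Cycle 1 Days 8 and 15, Cycle 2 Days 1, 8 and 15, Cycle 3 Days 1 and 8, and Day 1 of each later cycle.

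On analysis, SAP 12.3 summarises hematology by dose level and schedule, with a shift from baseline to the worst grade. It states: "Both scheduled and unscheduled post-treatment visits will be considered in tabulation of the worst post-treatment value".

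**The concern.** A visit with a heading and a window but nothing to do cannot be carried out as written. Sites cannot tell whether the marks were lost or the column was left in by mistake.

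The blank falls where a count would matter. The protocol synopsis says: "Since neutropenia has been observed in preclinical safety studies and is an anticipated toxicity in humans". It also says that additional schedules may be explored to reduce adverse events. Worst hematologic grades will be shown side by side by schedule. If one schedule is routinely sampled in the middle of its off period and the other is not, those columns do not rest on the same opportunity to observe a low count.

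**Working it through.** No figure in the plan has to be reproduced. The check maps the marks to days and compares the two tables.

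**Inputs.** Cycle length L is 21 days (Table 1) or 28 days (Table 9). Dosing is taken as Days 1–14 of each cycle; this is an assumption read from the schedule names. A routine count is a CBC mark or a Day 1 safety panel. End-of-treatment and follow-up visits are left out, because they can fall on any day. In Table 9, Day 15 has a +2-day window. In both tables a new cycle may start up to 3 days late, and its Day 1 assessments may be done up to 2 days early.

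**Days since the last dose.** A count on Day D > 14 falls D − 14 days after the last dose. A count on Day 1 of the next cycle falls L − 14 + 1 days after it.

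- Day 15: 15 − 14 = 1. Day 22: 22 − 14 = 8.
- Next Day 1, Table 1: 21 − 14 + 1 = 8.
- Next Day 1, Table 9: 28 − 14 + 1 = 15.

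| Dosing block | Table 1 counts (days after last dose) | Table 9 counts (days after last dose) |
|---|---|---|
| Cycle 1 | 1, 8 | 1, 8, 15 |
| Cycle 2 | 1, 8 | 1, 15 |
| Cycle 3 | 8 | 1, 15 |
| Cycle 4 onward | 8 | 15 |

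**With windows, Table 9 after Cycle 1.** Day 15 covers 1 to 1 + 2 = 3 days. The next Day 1 covers 15 − 2 = 13 to 15 + 3 = 18 days. Days 4–12 have no routine count. In Table 1 the next Day 1 covers 8 − 2 = 6 to 8 + 3 = 11 days.

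**Number of counts.** Through day 84 from Cycle 1 Day 1, Table 1 has 8 (days 8, 15, 22, 29, 36, 43, 50, 64). Table 9 also has 8 (days 8, 15, 22, 29, 36, 43, 57, 71). The difference is in timing, not number.

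**Distance from an assumed nadir to the nearest count.** For a nadir n days after the last dose of Cycle c, the nadir day is (c − 1) × L + 14 + n. The distance is the smallest absolute difference to a nominal count day. For example, with n = 8 in Cycle 2, Table 9 gives day 28 + 22 = 50; the nearest counts are days 43 and 57, so the distance is 7. Table 1 gives day 21 + 22 = 43, which is Cycle 3 Day 1, so the distance is 0.

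| Nadir n | Table 1, Cycles 1/2/3/4 | Table 9, Cycles 1/2/3/4 |
|---|---|---|
| 1 | 0/0/7/7 | 0/0/0/14 |
| 4 | 3/3/4/4 | 3/3/3/11 |
| 5 | 3/3/3/3 | 3/4/4/10 |
| 8 | 0/0/0/0 | 0/7/7/7 |
| 11 | 3/3/3/3 | 3/4/4/4 |
| 12 | 3/3/4/4 | 3/3/3/3 |

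In Cycle 1 the two schedules are equal in every row. In Cycles 2 and 3, Table 9 is farther from the nadir for n = 5 to 11. For n = 0 to 4 it is equal in Cycle 2 and closer in Cycle 3. In Cycle 4, Table 1 is closer for n = 0 to 11.

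**If Cycle 2 Day 22 were marked.** Counts through day 84 rise from 8 to 9. For n = 8, the Table 9 distances become 0/0/7/7, so only Cycle 2 changes.

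**The case against.** A reader might infer that worst hematologic grades will look better on 2 on/2 off than on 2 on/1 off. The documents do not support that, for four reasons.

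- No nadir time is given. The only related text is that the off-week allows for marrow recovery, so a count at 8 days may be a recovery count rather than a nadir count. For an early nadir, Table 9 does better in Cycle 3, because it has a Day 15 count that Table 1 lacks.
- The worst grade is taken over all cycles. Both schedules have a count 8 days after the first dosing block, so a worst grade seen there is captured on both. SAP 7.3 and 12.3 also admit unscheduled values.
- The DLT period ends with Cycle 1 (SAP 12.1), and Cycle 1 Day 22 has a CBC.
- SAP 7 excludes formal comparison between schedules, and a true difference from the second off-week is possible.

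A reader might also infer that detection is halved. Suppose a cytopenia of d ≤ 7 days starts at a uniformly random time in the 14-day off period. A count then catches it with probability d/14 without Day 22 and d/7 with it (36% against 71% for d = 5). But nothing in the documents supports uniform onset, and the sum compares Table 9 with itself, not with Table 1.

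Finally, the blank may be a leftover heading. Table 7, the other 28-day schedule, has a CBC at Cycle 1 Day 22 and no Cycle 2 Day 22 column at all. That would make the column an editorial slip, but it would still need correcting, and the timing difference between Tables 1 and 9 would remain.

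**Conclusion.** Two things are established. The Cycle 2 Day 22 column of Table 9 is empty and unexplained. After Cycle 1, routine counts on that schedule leave days 4–12 after the last dose uncovered, whereas Table 1 samples at 8 days throughout. The consequence is conditional: cytopenias on 2 on/2 off may be under-ascertained after Cycle 1 if the nadir falls about 5–11 days after the last dose. The direction and size of any bias in the worst-grade tables are not established, and Cycle 1 and DLT ascertainment are not affected.

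This rests on dosing on Days 1–14 and on the table as extracted from PDF. The CBC and vital-sign rows line up with the headers and agree with each other, so an extraction fault is unlikely. The correction is worth making because it is cheap and concerns the anticipated toxicity.

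**What to change.** 1. **Table 9.** Reconcile the Cycle 2 Day 22 column with Cycle 1 Day 22. Either carry over the CBC-with-differential and vital-sign marks, or delete the column if no visit was intended. The sponsor must say which was meant. Marking it costs one local CBC and a set of vital signs at a visit already listed, and repairs Cycle 2 only. Deleting it costs nothing and leaves the sampling as it is.

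2. **SAP 12.3.** Add a worst-grade shift table for hemoglobin, neutrophils and platelets, by dose level and schedule, over a common window from Cycle 1 Day 1 to about Day 22, allowing for visit windows. On the 21-day schedules the window must include the pre-dose Cycle 2 Day 1 count. A strict cut at the end of Cycle 1 would drop the 8-day count for 2 on/1 off and keep it for 2 on/2 off. With this window all five schedules have counts at about Days 7–8, 15 and 22. The cost is one extra output from data already collected.

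The new table has a limit that its footnote should state. Through Day 21 the 2 on/1 off and 2 on/2 off regimens are the same, so for that pair it gives a like-for-like reference and cannot show an effect of the second off-week. Differences that appear only in the all-cycle table should be read with the sampling days in view.
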